## **6. Devices**

The rationale for choosing the torque motor and laser for these studies rests on our long, safe experience with both these devices. In addition, there are practical advantages to these exact devices versus similar devices. Both devices were classified as non-significant risk devices, as described below. In the case of the non-painful somatic stimulation, an electric stimulator was chosen which is FDA-approved. The skin conductance coupler was chosen because of its widespread use to measure autonomic activation, and its classification as a non-significant risk device (see Application Section 23).

### **Torque Motor**

The robot is used to examine the adaptive control of reaching in force fields. Briefly, the subject holds onto the handle of a robotic arm and reaches to targets that are displayed on a video monitor. A sling was used to support the subject's arm and restrict movements to the horizontal plane. The subject reaches to targets which appear 10 cm from the center of the monitor at 1 of 4 angles. At the start of each trial, the subject holds the cursor at a crosshair which indicates the beginning of a trial. The crosshair then disappears and a square box target is displayed which the patient reaches to. A precision (torque) motor is used to produce a force to impede or assist the reaching movement. The subject's response to the force is measured as an indicator of the subject's ability to adapt his movement to changing conditions. At the end of each reach, the subject receives color and sound feedback on the speed and duration of his/her reach.

The mechanical design of the robot places its area of operation so it is impossible for the machine to hit the subject's torso, head, or legs. The only area where the robot could potentially impact the volunteer is in the hand or arm area. To prevent this, multiple procedures have been set in place. 1) The volunteer has a panic button that upon pressing will disable power to the actuators.

Date: February 19, 2023

Principal Investigator: [name].

Application Number: NA\_00079932

This disables the robot and makes it a passive system. 2) The experimenter also has a panic button that duplicates the action of the volunteer's panic button. 3) The robot is under computer control. Software continuously monitors the position of the robot's handle. If the robot leaves a small operating workspace, power is shut down to the robot's actuators.

Because of these characteristics this device does not meet the definition for a significant risk device which is a device having the 'potential for serious risk to the health, safety, or welfare of a subject' (Website of the JHM Office of Human Subjects Research - IRB: Investigational Medical Devices ). 'Such devices do not have to comply with FDA premarket approval and performance standards prior to use in research studies', like the present research study.

### **Laser**

Cutaneous heat stimulation will be delivered by a portable semiconductor laser (see Application Section 23). The stimulus intensity will be adjusted to elicit a sensation similar to a pinprick and a visual analog scale of intensity reading of 3-4/10 (usually 10-13 Watts/mm^2). At these parameters, a component of mechanical, warm or heat sensation is not reported spontaneously or in response to direct questioning. In order to avoid sensitization, the laser beam will be moved at random to a slightly different position for each stimulus. During the entire recording session continuous white noise will be delivered to each ear through earphones (Click-tone module - Grass Instruments, Co., Quincy, Mass. U.S.A.).

The risks of this portion of the protocol are minimal. The use of the laser to produce a pain stimulus is associated with a risk of burning the skin. The characteristics of the short duration laser pulses to be used in this study are well known. There have been no unintentional burns in our extensive experience over the past thirteen to thirty-two years in research studies of patients in the epilepsy monitoring unit and the laboratory of Drs. [name] and [name]. However, reddening of the skin (Grade 1 Burn or Sunburn) may occur at sites where the laser is applied (freckling). These have always resolved within a few days in our experience. Additionally, the laser poses a risk to vision if laser light enters the eye. During these studies, as in the past, all persons in the room will wear glasses and the signs will be posted on the door warning that the laser is in use and that entry is forbidden.

Because of these characteristics this device does not meet the definition for a significant risk device which is a device having the 'potential for serious risk to the health, safety, or welfare of a subject' (Website of the JHM Office of Human Subjects Research - IRB: Investigational Medical Devices). 'Such devices do not have to comply with FDA premarket approval and performance standards prior to use in research studies', like the present study.

### **Electrical Stimulator**

In this protocol, a primary outcome is to assess the effect of painful and non-painful somatic stimuli upon ongoing and evoked activity recorded from the cortex and the thalamus. We have now decided on electrical stimulation of the skin as the non-painful somatic stimulus. This stimulation will be applied to the wrist in order to produce a non-painful tingling sensation. For this purpose, we propose

Date: February 19, 2023

Principal Investigator: [name].

Application Number: NA\_00079932

to use a constant current stimulator (DS7A, Digitimer, Hertfordshire, UK) which is FDA approved with a 510(k) letter (Application Section - Devices). The electric stimulus will be delivered through a pair of Ag/AgCl electrodes filled with isotonic paste (9mm diameter, Docxs Biomedical Products, Ukiah, CA) placed at the wrist. The PI has long experience with devices of this type. Another electric stimulator (S12, Grass, Warwick, RI, U.S.A.) will also be used. This S12 stimulator has been used to stimulate on human cortices in UCLA (Schrader LM et al. 2006).

The risks of this stimulus are minimal. The subject will be free to remove the electrodes from his/her wrist at any time. Electrical stimulation of the skin and peripheral nerves has been carried out routinely with this and similar devices in Clinical and Research Neurophysiology laboratories around the world for many years. Finally, the electric stimulator for this study has recently been calibrated and certified for use in this protocol by the Clinical Engineering Service (CES) at the Johns Hopkins Hospital. The approval letter from the JHH CES can be found in Section 23 of the application.

As a local example of the safe use of these devices, the Department of Neurology at NINDS-NIH, under the direction of [name], has four decades of experience with the use of this and similar devices. These devices have been safely used by [name] to produce electrical stimulation of skin and peripheral nerves to investigate a wide range of research questions.

### **Contact Thermal Stimulator**

Quantitative sensory testing is carried out with the Medoc System, which delivers thermal stimuli through a thermode (inch square) placed on the skin. This sensory testing system will be used to determine warm/cold detection thresholds and heat/cold pain threshold. These tests will take about 10 minutes for one set of thresholds. As soon as the subject presses the button to indicate the detection or the pain threshold the temperature will return to 32°C baseline temperature. In addition, the thermode will be computer controlled and has built-in controls to prevent injury. The subject can remove the hand from the device at any time.

The risks of the protocol are minimal. The characteristics of this device are well known since it has been used around the world for decades without reports of injury. However, reddening of the skin may occur at sites where the thermode was applied. These have always resolved within a matter of hours.

Because of these characteristics this device does not meet the definition for a significant risk device which is a device having the 'potential for serious risk to the health, safety, or welfare of a subject' (Website of the JHM Office of Human Subjects Research - IRB: Investigational Medical Devices). 'Such devices do not have to comply with FDA premarket approval and performance standards prior to use in research studies', like the present study.

Medoc devices have been used safely to produce controlled thermal and painful stimuli over a twenty year period at numerous centers worldwide. Specifically, these devices have been used safely over to be a sixteen year period in the laboratory of [name] (Dentistry, U Maryland). He has safely used several versions of this same device as in this protocol over that period. This protocol has been reviewed yearly and approved by the IRB in University of Maryland (Chairperson: [name]).

### **Transcranial Direct Current Stimulation (tDCS) Device**

Date: February 19, 2023

Principal Investigator: [name].

Application Number: NA\_00079932

We employ surface electrodes (TransQE from IOMED®, surface area: 25 cm^2) connected to a conventional tDCS device Phoresor® II Auto (Model No. PM850, IOMED®, Salt Lake City, Utah 84120, USA) to deliver DC current to the scalp via surface electrodes.

tDCS will be administered with a current strength of 2 mA for maximum of 10 min by a constant current stimulator. Based on subject restrictions two types of electrode configuration will be applied:

1. Conventional rectangular sponge pad: we will use a pair of saline-soaked surface sponge electrodes (anode: 7 × 5 cm^2; cathode: 7 × 5 cm^2). The anode electrode will be positioned over the motor cortex representational area of the hand region on an affected side, and the return electrode will be placed above the contralateral motor cortex area.

2. 4 × 1 ring: The central active electrode will be placed above the representational area of the unaffected side hand (coinciding with the center of the anodal pad used for regular-pad stimulation) and surrounded by four return electrodes (each at a ring center to ring center distance of 3.5 cm from the active electrode) which will be connected to a four-to-one wire adaptor for the DC stimulator. Altogether five sintered Ag/AgCl ring electrodes (outer radius: 12 mm, inner radius: 6 mm) will be stabilized with plastic holders filled with EEG conducting gel (H + H Medical Devices, Germany and with gel-skin contact area ~25 ± 2.5 mm^2). Since the sensation to tDCS could differ with electrode and gel type (Minhas P, et al. 2010), here we will apply the suggested Ag/AgCl sintered ring electrodes (Minhas P, et al. 2010), and the conducting gel for less skin sensation as reported by the subjects.

Numerous methods utilize external landmarks to locate the motor strip (pre central gyrus). The motor strip typically lies anywhere from 4 to 5.4 cm behind the coronal suture. Based on the International 10/20 EEG system the C3 and C4 locations correspond to the left and right motor cortex (Edwards et al., 2013; Kido et al., 1980; Sarmento et al., 2008; Ebeling et al., 1987).

### **Skin Conductance Coupler**

In this protocol, we describe psychological measures of cognitive or affective processes during conditioning. We now seek to assess Skin Conductance as a physiological indicator of the autonomic activation throughout all conditioning trials in this protocol. The skin conductance response will be assessed by use of a device which applies a small constant voltage between two electrodes and measures current to estimate conductance of the skin between the electrodes. This Skin Conductance Coupler (V71-23, Coulbourn Instruments, Boston MA) applies a constant 0.5 Volt potential through Ag/AgCl electrodes filled with isotonic paste (9mm diameter, Docxs Biomedical Products, Ukiah, CA). These electrodes are placed on the hypothenar surface of the subject's hand. To further assure that the electrical leakage current is within safe limits, a medical grade isolation transformer will be used between the wall plug and the device (Dale Technology Medical-Grade Isolation Transformers, NY, USA). Finally, the Skin Conductance device in this study has been calibrated and certified by the Clinical Engineering Service (CES) at the Johns Hopkins Hospital.

Date: February 19, 2023

Principal Investigator: [name].

Application Number: NA\_00079932

Because of these characteristics, this device does not meet the definition for a significant risk device which is a device having the ‘potential for serious risk to the health, safety, or welfare of a subject’ (Website of the JHM Office of Human Subjects Research - IRB: Investigational Medical Devices). Such (non-significant risk) devices do not have to comply with FDA premarket approval and performance standards prior to use in research studies’, like the present study.

### **Auditory Equipment Description**

Speech recording is carried out with the Zoom System (Zoom H6 - 6 simultaneous track recording, 4 balanced inputs) and a high quality microphone is employed during recording (Preosonus PRM1 Precision Flat Frequency Microphone). Also, in order to increase the quality of the recorded speech signal a high quality audio cable is used (High-quality, braid shield XLR, Monster Performer 600 Mic Cable).

### **Respiratory Effort Sensor**

The SleepSense Piezo Crystal respiration sensor (respiratory effort sensor based on piezoelectric crystal technology) is used to measure the temporal pattern of speech production including the initiation of speech. The Piezo Crystal respiration effort sensor is made from a piezoelectric crystal that generates a small electric potential in response to stress and movement and converts chest or abdominal respiration motions to an analog voltage that provides an indication of respiration waveform. The SleepSense Piezo Crystal respiration sensor is designed with an electrically isolated piezo element to increase immunity to environmental artifacts and provide improved signal stability if the sensor shifts spatially throughout the respiratory displacement. The sensor bands are strapped around the patient’s abdomen or chest, and do not make contact directly with the patient’s skin.

### **Direct Cortical Stimulation Equipment**

a) The Alpha Omega Neuro Omega clinical data acquisition system (Bethlehem, Israel) is a physiological navigation system intended for different neurosurgery and neurophysiological clinical applications, including recording from and stimulating brain motor and sensory neurons to accurately navigate for neurosurgery target localization during the treatment of movement disorders and to aid in the placement of deep brain stimulation leads. The system is capable of recording from and stimulating various areas of the brain (deep structures and cortex). The system is FDA approved for these purposes, and in this protocol will be used for performing single unit recordings from subcortical structures, macrostimulation (via the guard-ring element of an implanted microelectrode) of subcortical structures, cortical electrocorticography recordings, and cortical direct current stimulation.

b) The Blackrock Microsystems CereStim R96 is a fully programmable neurostimulator designed for the Blackrock Microsystems data acquisition system (Neural Signal Processor) with 96 output channels and the capability of producing up to 16 simultaneous electrical stimuli. The biphasic current pulses generated by the CereStim R96 are intended to stimulate neurons through surface contacting macro-electrodes. The CereStim 96 comes with the Stim Manager Software and both Matlab SDK and C++ SDK. Stim Manager operates in two modes: Manual and Program. Control of the stimulator through C++ or Matlab APIs provides a simple path for integration of the stimulation system directly

Date: February 19, 2023

Principal Investigator: [name].

Application Number: NA\_00079932

into experimental control systems. The user first selects an electrode from the Electrode Array Panel (1-96) and then creates a custom stimulus in the Waveform Panel. The latter allows the user to specify single-stimulation parameters by defining individual phases including polarity, number of pulses, inter-phase delay, amplitudes, phase width and frequency. The CereStim R96 is an additional utility to the existing Blackrock data acquisition system. It is currently approved by the Johns Hopkins Medicine IRB under protocol IRB00040308 for direct cortical stimulation applications during invasive epilepsy monitoring.

## 7. Study Statistics

This is a single institution, long-term exploratory study to understand forebrain networks of human sensory processing and motor control. Specifically Objective I will address cortical and subcortical networks of sensory signaling and processing, while Objective II will address the cortical and subcortical networks involved in motor control.

Due to the exploratory nature of the study, all outcome data will be collected regardless of data type such as electrophysiological responses, or timing, or the questionnaires related psychological function. In general, data will be summarized using descriptive statistics and graphical techniques. Within and between-subjects comparisons will use paired and unpaired analysis, respectively. Longitudinal outcomes or repeated measures will be considered and possibly be analyzed using generalized linear model. Correlation coefficient or concordance correlation coefficient will be used to estimate correlation between two outcomes.

The outcome measures for the three objectives are indicated below:

Primary and secondary outcome variables:

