We also aim to explore the influence of single nucleotide polymorphisms (SNPs) upon sustained attention to pain and the magnitude of the vigilance decrement. We will first evaluate the effects of common SNPs known to influence pain perception, fear of pain, error processing during performance of a cognitive tasks (Witte AV and Floel A 2012; Bonenberger, et al 2015; Gurvich C and Russell SL 2015; Forsberg JT, et al 2018). Pain related SNPs will also be examined including: catechol-O-methyltransferase (COMT) Val158Met, the serotonin transporter promoter long or short tail mutation (5-HTTLPR), and mu opioid receptor gene (OPRM1) Asn40Asp. These predictions will be carried out on baseline genotype measurements and used for DNA extraction and analysis.

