### Objective III: Sensory Processes: Behavioral Tasks

These tasks will include attention tasks and a learning task which involves the painful and nonpainful stimuli, as described above under *Sensory Processes: Sensory stimulation*, including Heat Stimuli (Laser -2 and Thermode-3), and Electrical Stimuli-7. Attentional protocols will be carried out in one session, often with presentation of a painful (laser, thermode, or electrical), and a nonpainful (electrical or thermode) stimulus presented in a single train in random order. The subject is instructed to either: i) count or ii) push buttons in response to the painful stimulus (attention to pain), or the non-painful stimulus (distraction from pain) or both, as presented in random order and counterbalanced across patients. In three other tasks, a single train will consist of: i) only nonpainful stimuli which the patient counts, ii) only painful stimuli which the patient counts and iii) only painful stimuli while the patient performs a cognitive task, e.g. reading for comprehension.

Some subjects in both categories will be involved in protocols for classical conditioning or learning, which occurs when a neutral conditioned stimulus (CS+, a light or sound) is paired with an unconditioned aversive or appetitive (reward) stimulus (US). In the case of aversive conditioning, the US might be the painful cutaneous laser, thermode, or electrical stimulus, while in appetitive conditioning it might be a reward of one dollar. As measures of psychological variables, we propose to administer psychological questionnaires including depression, anxiety and PTSD scales.

Under Objective I extra-operative studies will often be carried out over a two hour session during which painful and nonpainful stimuli will be presented in a single train. During the extra-operative conditioning protocol, two or three sessions may be carried out on different days. Within each session there will be rest periods and between two and six separate trials with either attentional or conditioning tasks. The length of the intraoperative sessions will be less than one hour in length.

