## **8. Risks**

As in previous studies, the main risk of intra-operative tests is identified as the fatigue associated with additional testing at several recording sites during the localization procedure. Therefore, the main risks of the operation are associated not with the research tests, but with the standard surgical procedure.

In addition, the somatic sensory, motor, and psychological tests may be applied during extra-operative testing in all patients and healthy subjects. These tests are associated with relatively minor risks during both intra-and extra-operative testing. These risks are listed below by the category of testing. The tests, or combinations of tests, below in this section, and in the section above on 'Research testing procedures ...', are numbered using the same system as is used in the Consent.

Date: February 19, 2023

Principal Investigator: [name].

Application Number: NA\_00079932

None of these risks has resulted in a patient injury in the many years in which these research procedures have been performed for prior studies. All subjects will have the option to withdraw from the protocol at any time without penalty.

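### Attention conditions are counterbalanced over one session, but Section 7 names no order or period term, so any drift over the session stays in the error of a plain paired comparison and costs precision

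*Combined protocol and SAP*

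**What the plan says.** **Design.** Section 4, under Objective III: Sensory Processes: Behavioral Tasks, states: "Attentional protocols will be carried out in one session". Subjects are told to respond to the painful stimulus, to the non-painful one, or to both, "as presented in random order and counterbalanced across patients". The same section adds: "Within each session there will be rest periods and between two and six separate trials with either attentional or conditioning tasks". It does not give the number of orders or the number of patients per order. The effect of attention is part of the secondary outcome of Objective I (Section 2).

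**Analysis.** Section 7 states: "Within and between-subjects comparisons will use paired and unpaired analysis, respectively". The next sentence reads: "Longitudinal outcomes or repeated measures will be considered and possibly be analyzed using generalized linear model". Neither sentence names an order, period or sequence term, and none appears elsewhere.

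**Change over a session.** Section 3, under Objective I: Sensory Processes, plans to study genetic influences on "sustained attention to pain and the magnitude of the vigilance decrement". Section 8 says that "the main risk of intra-operative tests is identified as the fatigue associated with additional testing at several recording sites". Neither gives a size.

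**The concern.** Counterbalancing spreads any time-on-task effect evenly over the conditions, so the mean condition difference is not shifted. It does not make that effect disappear. Suppose responses fall from the first to the second position in the session. Subjects who attend to pain first then have their difference pushed one way, and those who attend to pain second have it pushed the other way. A plain paired analysis treats this systematic split as random scatter between subjects. An analysis that knows each subject's order removes it.

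At stake is the precision of the attention contrast. The design already does the work of balancing on order, and the stated analysis does not commit to using it. Intra-operative samples may be small, and there avoidable noise matters most.

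**Working it through.** The plan has no sample size calculation, alpha, power or effect size, so there is no figure of its own to reproduce. The check below is an illustration with two conditions and two orders.

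**Inputs**
- From the documents: one session, counterbalanced order, paired analysis, no order term. The only patient count for sensory testing is seventy, spread over one or more tests (Section 4, Objective II: Sensory Processes: Sensory Stimulation). It is not specific to the attention task.
- Assumed: two-sided alpha 5%; SD of the within-subject difference, given order, equal to 1; condition effect tau of 0.75, 0.66 and 0.50 at N = 16, 20 and 34, chosen so that the paired test has about 80% power with no order effect; order effect pi from 0 to 1 SD.

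**Model.** For subject i, D_i = tau + s_i·pi + e_i, with s_i = +1 or −1 by order and e_i ~ N(0, 1). Here pi is the shift between first and second position.

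**Equal order groups.** The mean of D estimates tau without bias.
- Plain paired analysis: variance about 1 + pi², so interval width grows by √(1 + pi²), and the sample size needed grows by about 1 + pi².
- Order-adjusted analysis (mean of the two order-group means): SE = 0.5·√(1/n1 + 1/n2), which is 1/√N when n1 = n2, on N − 2 degrees of freedom. It does not depend on pi.

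Simulated results for N = 16, 20 and 34:

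| pi (SD) | 1 + pi² | Width factor | Paired power | Adjusted power |
|---|---|---|---|---|
| 0 | 1.00 | 1.00 | about 80% | about 80% |
| 0.25 | 1.06 | 1.03 | about 78% | about 80% |
| 0.5 | 1.25 | 1.12 | 72–74% | about 80% |
| 1 | 2.00 | 1.41 | 49–52% | about 80% |

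With no attention effect, the paired test is conservative: its actual alpha is about 3% at pi = 0.5 and below 1% at pi = 1. A separate run at N = 70 with tau = 0.335 gave the same pattern: 78.8%, 77.0%, 71.4% and 49.1% down the rows, against 78.9% adjusted.

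**Unequal order groups, no attention effect, pi = 0.5.** Bias of the paired mean = pi·(n1 − n2)/(n1 + n2).

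| Split | Bias (SD) | Paired false positives |
|---|---|---|
| 12:8 | 0.5 × 4/20 = 0.10 | 4.4% |
| 40:30 | 0.5 × 10/70 = 0.07 | 5.9% |
| 11:5 | 0.5 × 6/16 = 0.19 | 8% |
| 14:6 | 0.5 × 8/20 = 0.20 | 10% |
| 23:11 | 0.5 × 12/34 = 0.18 | 12% |
| 45:25 | 0.5 × 20/70 = 0.14 | 16% |

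At pi = 1, the three splits near 70:30 (11:5, 14:6 and 23:11) give about 10%, 16–17% and 24%. The adjusted test stays at 5% for these three splits. Averaged over simple random assignment of order, with no counterbalancing at all, the paired test's false-positive rate was 5.0–5.1%. The inflation is therefore conditional on a bad split.

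**The case against.** The strongest reply has four parts.

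1. **Section 7 does not stop at paired analysis.** Several attention conditions in one subject are repeated measures, and a generalized linear model can carry an order term. A reader might infer that the paired sentence binds every within-subject comparison; the following sentence rules that out. But that sentence is tentative and lists no terms, so the gap in specification stands.

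2. **The protocol does not say that drift is strong.** A reader might infer that it expects large within-session change. Fatigue is listed as a participant risk and the vigilance decrement as a topic of study, both without a size. The Laser text in Section 6 describes moving the beam to avoid sensitization, which is mitigation and no evidence of drift. Rest periods are planned within sessions. This part stands in full: the order effect could be small.

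3. **Unequal orders run against the design.** A reader might infer that the attention results will be biased with too many false positives. Counterbalancing aims at near-equal groups, and nothing in the documents suggests that it will fail. Even under simple randomisation, a split at least as extreme as 11:5, 14:6 or 23:11 has probability 21%, 12% and 6%. This part also stands.

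4. **The design is partly inferred.** The text does not state plainly that every subject performs every instruction. Stimuli within a train are already said to be in random order, so counterbalancing across patients most naturally refers to the instructions, but this is a reading. The same randomisation means that the painful versus non-painful contrast within a train is largely unaffected.

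**Conclusion.** The point holds as a loss of precision of unknown size. It is negligible at an order effect of 0.25 SD or less (about 2 power points), noticeable at 0.5 SD (about 7 points) and large at 1 SD (about 30 points). These figures rest on the assumed order effects and sample sizes and on a case with two conditions and two orders. Sessions may hold up to six trials, and that case was not simulated.

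The documents do not support a claim of bias or of an inflated false-positive rate in the planned analysis; that would need achieved orders to end up markedly unequal, roughly 70:30 in small samples. Nor is a power statement broken, because the study is declared exploratory and makes none. What remains is a contrast within a secondary outcome that is analysed less efficiently than its own design allows, and that can be improved at almost no cost.

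**What to change.** In Section 7, state that comparisons between counterbalanced attention conditions use a linear mixed model with condition and period (position in the session) as fixed effects and subject as a random effect. For two conditions, this can be the condition difference adjusted for order group. Record each subject's order, and report the number of subjects per order so that a reader can see whether the balance was achieved.

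**Cost.** Wording, one recorded variable, and one degree of freedom per order or period term. At N = 16 with two orders and no order effect, power went from 79.8% to 79.4%. If the groups turn out unequal, the variance of the adjusted estimate rises by (n1 + n2)²/(4·n1·n2), for example 4900/4500 = 1.09 at 45:25. No extra patients, tests or session time are needed.

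**Limit.** A period term does not remove differential carryover, where one instruction affects responses under the next.
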